## Study Title

Comparison between Retrolaminar block combined with Erector Spinae Plane block, and Erector Spinae Plane block **alone** for **post-thoracotomy pain**.

## Introduction

Post-thoracotomy pain is a challenging clinical problem that may be associated with increased morbidity and mortality. (1)

The surgical incision produces post-thoracotomy pain (PTP) via damage to the ribs and intercostal nerves, inflammation of the chest wall, pleura or pulmonary parenchyma cutting, and placement of the intercostal chest tube. Acute PTP inhibits the ability to breathe and cough normally. Numerous analgesic techniques are used to relieve PTP, including systemic opioids, regional techniques (such as paravertebral nerve blockade, intercostal nerve blockade, intrapleural analgesia, and epidural opioids with or without local analgesia), cryo-analgesia, and transcutaneous electrical nerve stimulation (TENS). (2)

Emerging research has shown that the novel erector spinae plane block (ESPB) can be employed as a simple and safe alternative analgesic technique for acute post-surgical, post-traumatic, and chronic neuropathic thoracic pain in adults. (3)

ESPB was first reported in 2016 for ipsilateral thoracic analgesia. (4) It was found to be a safe and effective block that can be performed by an emergency physician in the emergency department setting for addressing acute pain due to multiple rib fractures. (5)

Retrolaminar block (RLB) was first reported in 2006 as an alternative approach to PVB. RLB is performed with US imaging or the landmark technique. (4) The efficacy of continuous RLB has been reported for breast cancer surgery . (6)

However, the efficacy of ESPB has been described in a greater number of clinical reports than has RLB: a rib fracture, breast surgery, thoracoscopic surgery, lumbar spinal surgery, and laparoscopic abdominal surgery. In contrast to RLB, most of the literature on ESPB reported the use of the single-shot technique (80.2%). The local anesthetic was postulated to infiltrate the ventral and dorsal rami of the spinal nerve. However, Ueshima et al. reported that ESPB could not provide adequate analgesia of the anterior branch of the intercostal nerve. (4)

The rationale of the study is that to the best of our knowledge each of ESPB and RLB has limitations regarding sensory block and distribution so our hypothesis is combining both will provide more solid block regarding sensory distribution, time interval of the block efficacy, and postoperative morphine consumption in patients undergoing thoracic surgeries.

Few studies evaluated the efficacy of ultrasound (US) guided erector spinae plane block on post-thoracotomy analgesia, however for the best of our knowledge no one compared the effect of ultrasound (US) guided retrolaminar block combined with erector spinae plane block and ultrasound (US) guided erector spinae plane block alone in patients undergoing thoracic surgeries.

### **Aim of the work**

This work aims to investigate whether adding the RLB to the ESPB would intensify the block decreasing the primitive opioid consumption. **Using 20ml for ESPB compared to 10ml ESPB adding to 10ml RLB.**

### **Objectives:**

To **assess** the efficacy of ultrasound (US) guided Retrolaminar block combined with Erector Spinae plane block compared to ultrasound (US) guided solo Erector Spinae plane block for thoracotomy pain.

### **Hypothesis:**

We hypothesize that ultrasound (US) guided Retrolaminar block combined with Erector Spinae plane block will provide more post-operative analgesia than ultrasound (US) guided Erector Spinae plane block alone for thoracotomy pain.

### **Ethical Considerations**

The study will be conducted after taking approval from the research ethical committee; Informed consent will be obtained from the patients. Documentation of any complications -if present- will be documented.

### **Methodology**

#### **I. Study design**

This is a randomized controlled, double-blind study.

#### **II. Study setting and location**

The study will be conducted at Kasr Al-Ainy Hospital, Faculty of Medicine, Cairo University, cardiothoracic **unit**.

#### **III. Study population:**

Patient undergoing **open** thoracic surgery **through a posterolateral thoracotomy**.

## IV. Eligibility Criteria

### 1. Inclusion criteria

- Age from 18–65 years.
- body mass index (BMI) ranged between 20 and 40 kg/m^2
- ASA I, II patients undergoing **open thoracic surgery through a posterolateral thoracotomy**

### 2. Exclusion criteria

- Patient refusal.
- Sensitivity or contraindication to **local anesthetic drugs**.
- History of psychological disorders and/or chronic pain.
- Localized infection at the site of the block.
- Coagulopathies, **patients on anticoagulants and antiplatelets**, and significant liver or renal insufficiency.

## V Study Procedures

### 1. Randomization

Patients will be allocated in a parallel manner into two equal groups: Group 1 (ESPB (control group): (n = 15) patients will receive preoperative US-guided ESPB on the operated side by 20 ml bupivacaine 0.25%. Group 2: US-guided ESPB with 10 ml bupivacaine 0.25% + the US-guided retrolaminar block 10 ml bupivacaine 0.25% group: (n = 15) on the operated side.

Randomization will be accomplished through the use of computer-generated random numbers and closed opaque envelopes. Another anesthesiologist who will not be involved in the other parts of the study will open the envelopes to enroll patients. and both patients and outcome assessors will be blinded to the assignment of groups.

### 1. Study Protocol

Preoperative assessment of all patients comprised of history taking, clinical examination, laboratory testing (complete blood count, kidney function tests, liver function tests, prothrombin time, and partial thromboplastin time), electrocardiogram, and chest X-ray. The study protocol will be explained to the patients, and their consent will be obtained. All patients will be made familiar with the use of the pain score; visual analog scale score (VAS) identifying 0 as no pain and ten as the worst possible pain.

The patients will be continuously monitored in the holding room for **heart rate**, blood pressure, and oxygen saturation (baseline values). An intravenous (IV) 18-

gauge cannula will be inserted. Midazolam **2mg boluses** IV will be administered for each patient. Patients will receive US-guided ESPB and US-guided ESPB + US-guided Retrolaminar plain block before induction of GA.

US-guided ESPB Blocks will be performed with a US machine (Philips HD 11xe) equipped with an HFL38X high-frequency linear transducer (13–16 MHz). With patients in a sitting position, the transducer will be positioned longitudinally 3 cm lateral to the T5 spinous process. The trapezius, rhomboid major, and erector spinal muscles will be revealed superficial to the shadow of the hyperechoic transverse process. Then, 3 ml lidocaine 2% will be used to anesthetize the skin. Using a 20-gauge block needle **inserted** in-plane in a cephalad-to-caudad orientation to position the tip into the fascial plane on the deep (anterior) side of the erector spinae muscle, 20 ml bupivacaine 0.25% will be injected. The needle tip's placement was confirmed by observable fluid spread lifting the erector spinae muscle away from the transverse process's bony shadow. (2)

For the retrolaminar block, an in-plane technique under ultrasound guidance will be used to advance the needle towards the posterior surface of the T5 lamina in a cephalic to caudal direction until contact with the lamina will be made. After confirming contact, the correct spread will be verified by injecting 1.0–2.0 ml of saline to create a plane of hypoechoic space on the posterior surface of the T5 lamina,(7) and 10 ml bupivacaine 0.25% will be injected.

**The block success will be assessed by a blind observer unrelated to data collection. The presence of the cold sensation in T1-T8 dermatomes in the blocked side after 30 minutes indicated a failed block, and the patient will be excluded . (9)**

GA will be induced for both groups using IV fentanyl 2 µg/kg and propofol 2 mg/kg. Tracheal intubation will be facilitated by Atracurium 0.5 mg/kg and will be done either by a left-sided double-lumen endobronchial tube (**Mallinckrodt's 35 to 41 F according to patient size**), or single lumen ETT and a fiberoptic bronchoscope will be used to ensure the correct position of the tube. The tidal volume will be adjusted to be 6–8 ml/kg, and the respiratory rate will be adjusted to keep the end-tidal CO2 between 30 and 40 mmHg.(2)

Anesthesia will be maintained with inhaled Isoflurane with MAC 1-1.5 in oxygen-enriched air (Fio2 will be adjusted to keep peripheral O2 saturation ≥90%) and top-up doses of Atracurium (0.1 mg/kg) IV will be administered as required. Ringer acetate will be infused to replace their fluid deficit, maintenance, and losses. (2)0

Additional bolus doses of fentanyl one  $\mu\text{g}/\text{kg}$  IV will be given if the mean arterial blood pressure (MAP) or heart rate (HR) rises above 20% of baseline levels after exclusion of all causes leads to an increase of both HR and MAP as awareness and fading of neuromuscular blockade.

One reading of MAP and HR will be taken before induction of GA to be defined as a baseline reading and then will be recorded immediately before surgical incision and at 30 min intervals intraoperatively. Hypotension will be treated with 100 ml 0.9% normal saline bolus and 5 mg ephedrine IV in incremental doses to maintain MAP above 70 mmHg. Bradycardia (HR <60) will be treated with 0.1 mg/Kg atropine IV.(2)

At the end of the surgery, the residual neuromuscular blockade will be reversed using 0.07 mg/kg Prostigmin IV, and extubation will be performed after complete recovery of the airway reflexes.

Then, patients will be transferred to the post-operative care unit (PACU) and will be observed for two hours. Following that, the patients will be transferred to a ward and given 1 g of acetaminophen IV every 8 hours, ketorolac tromethamine 30mg IM/12h as 2 components of multimodal anesthesia regimen for postoperative pain control. (10)

VAS (at rest and cough), MAP, and HR will be noted immediately on arrival to PACU (0 h) and at 2, 4, 6, 12,18, and 24 h postoperatively. Rescue analgesia will be provided in the form of IV morphine 3 mg boluses if VAS >3. The time to first request rescue analgesia and the total morphine administered during the first 24-hour postoperative will be recorded.

Patient satisfaction (satisfied or not satisfied) will be recorded 24 hours postoperative. Adverse events will be reported (PONV, hypotension, bradycardia, excessive sedation, and hematoma).

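### Patients with a failed block are dropped after randomization and treatment, so 24-hour morphine is compared in a subset selected on a result of the allocated block; size and direction of the effect are unknown

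*Combined protocol and SAP*

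**What the plan says.** Allocation comes first. Under Randomization, "Another anesthesiologist who will not be involved in the other parts of the study will open the envelopes to enroll patients". The allocated block is then given before induction of anaesthesia. Under Study Protocol, "The block success will be assessed by a blind observer unrelated to data collection". The criterion for failure is "The presence of the cold sensation in T1-T8 dermatomes in the blocked side". The consequence for a patient who meets that criterion is removal from the trial: such a finding "after 30 minutes indicated a failed block, and the patient will be excluded".

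Block failure is not an eligibility criterion. The only entry under Exclusion criteria that mentions the block is "Localized infection at the site of the block".

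Block quality is part of the hypothesis. The Aim of the work asks whether "adding the RLB to the ESPB would intensify the block decreasing the primitive opioid consumption", and the Introduction expects that "combining both will provide more solid block regarding sensory distribution, time interval of the block efficacy, and postoperative morphine consumption".

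The primary outcome is total morphine over 24 hours. Study Protocol states that "Rescue analgesia will be provided in the form of IV morphine 3 mg boluses" when VAS exceeds 3, and that the 24-hour total is recorded. The Sample size section raises 16 per group to 18 for dropouts without mentioning failed blocks. The Statistical analysis section names no analysis population, no reporting of failures by arm and no sensitivity analysis.

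**The concern.** Randomization makes the two groups comparable at allocation. Here membership of the analysed group depends on a sensory test taken after the allocated treatment, and the plan itself expects the added block to improve sensory block. It therefore supplies a reason for the proportion removed to differ by arm. Because morphine is given in response to pain, removed patients may also differ in the outcome.

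If the combination fails less often and failures use more morphine, exclusion discards part of its benefit. If it fails more often, exclusion hides that and flatters it. With no failures reported by arm, a reader of the results could not tell which had happened. If outcomes are not collected on excluded patients, the comparison of all randomized patients cannot be recovered later.

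**Working it through.** **Inputs from the Sample size section.** The ESPB mean and SD are printed with equals signs where decimal points belong; I read them as 8.52 and 4.29 mg. Target difference: 0.5 × 8.52 = 4.26 mg. Randomized per arm: 18. The step from 16 to 18 reproduces: 16/(1 − 2/18) = 18. The 16 does not: a two-sided t-test at power 0.95 needs 28 per group. That figure, and the 15 per group under Randomization, are separate matters on which this point does not depend.

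**Assumed inputs.** All failure rates, and mean morphine after failure (F), since the documents give none.

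**Formula.** For each arm let S be mean morphine after a successful block, f the failure rate and D = F − S. The mean over all randomized patients is S + f·D; after exclusion it is S. Exclusion therefore changes the difference (ESPB minus combination) by

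f_comb·D_comb − f_ESPB·D_ESPB.

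This is 0 if D = 0 in both arms, if f and D are each equal across arms, or if the two products happen to cancel. Equal failure rates alone are not enough.

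**20% ESPB v 5% combination, F = 14 mg.**
- 8.52 as the success mean in both arms: D = 14 − 8.52 = 5.48; change = (0.05 − 0.20) × 5.48 = −0.82 mg.
- 8.52 as the overall mean in both arms: success means are (8.52 − 0.2 × 14)/0.8 = 7.15 and (8.52 − 0.05 × 14)/0.95 = 8.23, a false difference of 1.08 mg against the combination.
- Range 0.82-1.08 mg, or 19-25% of 4.26 mg. Two-sided type I error is 0.085-0.105. At the upper end about 0.101 falsely favours ESPB alone and 0.004 the combination.
- With the rates reversed, shift and split reverse.

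**Other assumed cases.**
- 20% v 5%, F = 11: 0.37-0.49 mg against the combination; type I error 0.057-0.061.
- 20% v 5%, F = 5: 0.53-0.70 mg in favour of the combination; type I error 0.064-0.072.
- 10% v 5%, F = 11 to 14: 0.12-0.32 mg; type I error 0.051-0.055.
- F equal to the success mean: 0.
- 20% in both arms, F = 14 (ESPB) v 11 (combination), overall means 8.52: success means 7.15 and (8.52 − 0.2 × 11)/0.8 = 7.90, a false difference of 0.75 mg.

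Keeping all patients gives simulated type I error of 0.048-0.051.

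**Power of keeping v excluding** (simulated; success means 8.52 and 4.26 mg; failure rates are ESPB v combination; all-patient means are (1 − f)·S + f·F):

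| Failure | F (mg) | All-patient difference (mg) | Keep | Exclude |
|---|---|---|---|---|
| 20% v 5% | 14 | 9.62 − 4.75 = 4.87 | 0.84 | 0.76 |
| 10% v 5% | 14 | 9.07 − 4.75 = 4.32 | 0.76 | 0.79 |
| 20% v 5% | 5 | 7.82 − 4.30 = 3.52 | 0.64 | 0.76 |
| 20% v 20% | 14 | 9.62 − 6.21 = 3.41 | 0.47 | 0.72 |
| 5% v 20% | 14 | 8.79 − 6.21 = 2.59 | 0.32 | 0.76 |

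In the last three rows part of the fall comes from a smaller all-patient difference. In the 10% v 5% row that difference is slightly larger than 4.26 mg, so the small fall comes from greater variability.

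**Dropout allowance.** It covers two losses per arm. The chance of more than two failures among 18 is 27% at a 10% failure rate and 73% at 20%.

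**The case against.** The strongest reply is that a comparison among successful blocks may be what the investigators intend. The same cited source supports both the exclusion rule and the 8.52 mg planning value. Failure is judged at 30 minutes by a blinded observer, so the judgement cannot be informed by the 24-hour outcome. On that view there is no bias, only an unstated target.

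Part of this stands. Blinding limits discretionary exclusion, and a successful-block comparison is a legitimate secondary question. But blinding does not stop true failure rates from differing by arm. The Objectives, Hypothesis and Primary outcome do not restrict the question to successful blocks, and even that comparison would need failures reported by arm.

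It is also fair that the size is wholly assumed and that analysing everyone does not settle interpretation: the documents do not say what analgesia a failed-block patient receives, and the all-patient total depends on it.

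Two stronger readings are tempting. A reader might infer that exclusion inflates false positives for the combination. The documents do not support this: in the direction the Introduction expects, with failures using more morphine, the error falls almost wholly the other way, and a positive result would be conservative. A reader might also infer that keeping everyone costs no power. That holds in some assumed cases and fails in others.

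**Conclusion.** The structural point holds: the primary outcome is compared in a subset selected on a consequence of the allocated treatment, and nothing in the eligibility, sample size or analysis text restores the randomized comparison. Neither the blinded observer nor the dropout allowance cures this; the allowance replaces numbers, not comparability.

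Size and direction cannot be determined from the documents. On the assumed inputs the shift runs from 0 to about 1.1 mg in either direction, and type I error from near nominal to about 0.105. The case for changing the plan rests on the structure, the low cost and the risk of irrecoverable data, not on a particular size.

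Whether cold sensation in any or in all of T1-T8 counts as failure is also unstated. That is a separate missing detail, though it leaves the size of the excluded group open.

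**What to change.** In Study Protocol, replace the exclusion at the end of the block-success paragraph with: *the failed block will be recorded; the patient remains in the trial for 24-hour outcome collection and is analysed in the allocated group.*

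In Statistical analysis, add: *The primary analysis of 24-hour morphine includes all randomized patients in their allocated group; patients with no postoperative outcome because surgery was cancelled are reported by arm with reasons. Block failures, and the analgesia these patients received, are reported by arm. An analysis restricted to successful blocks is a sensitivity analysis.*

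This sets no analgesic regimen. Reporting the analgesia by arm is needed because the all-patient result depends on it.

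The cost is a few sentences, plus 24-hour morphine totals of a kind the protocol already records, on patients already randomized. Power may move either way, as tabulated above, so the sponsor should not assume that the change is free in power. The change should be made before outcomes on failed-block patients are lost.

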### **2. Secondary outcome(s).**

- **Pain score according to VAS score at 30min, 2h, 4h, 8h, 12h, 24h postoperative.**
- **Heart rate and MAP at 0 , 15min, 30min, 45min, 60min, 90min, 120min, then every 1h intraoperative.**
- **First request of analgesia postoperative.**
- **Opioid requirements intraoperatively.**
- **Incidence of complications as hypotension, bradycardia, postoperative nausea, vomiting (PONV) and pruritis.**

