#### 2) Statistical analysis

- Microsoft excel 2013 will be used for data entry and the statistical package for social science (SPSS version 24) will be used for data analysis.
- Simple descriptive statistics (arithmetic mean and standard deviation) will be used for the summary of normal quantitative data (median and interquartile range) for a summary of abnormal quantitative data and frequencies will be used for qualitative data.
- Bivariate relationship will be displayed in cross-tabulations and a Comparison of proportions will be performed using the chi-square and Fisher's exact tests where appropriate.
- **T-test** and post-hook tests will be used to compare normally distributed quantitative data and Kruskal-Wallis for skewed data.
- P value will be calculated to assess statistical significance, a value less than 0.05 will be considered statistically significant.

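### Intraoperative HR and MAP: outcome times and recording times disagree, the baseline is not placed before or after the block, and no baseline covariate is named

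*Combined protocol and SAP*

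**What the plan says.** The Study Protocol section (under V Study Procedures) has HR and blood pressure monitored in the holding room and labels these readings as baseline: "blood pressure, and oxygen saturation (baseline values". In the order of the text this comes before midazolam and before the block. On the block it says "Patients will receive US-guided ESPB and US-guided ESPB + US-guided Retrolaminar plain block before induction of GA".

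Later the same section gives a baseline definition: "One reading of MAP and HR will be taken before induction of GA to be defined as a baseline reading". After that, HR and MAP "will be recorded immediately before surgical incision and at 30 min intervals intraoperatively". Two treatment rules bear on these variables. Extra fentanyl "will be given if the mean arterial blood pressure (MAP) or heart rate (HR) rises above 20% of baseline levels", and hypotension is treated with saline and "5 mg ephedrine IV in incremental doses to maintain MAP above 70 mmHg".

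The Secondary outcome(s) section lists "Heart rate and MAP at 0 , 15min, 30min, 45min, 60min, 90min, 120min, then every 1h intraoperative", without defining time 0. Intraoperative opioid requirement is a separate item on that list.

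The Statistical analysis section gives one general rule for quantitative data: a t-test and post-hoc tests "will be used to compare normally distributed quantitative data and Kruskal-Wallis for skewed data". It names no analysis specific to HR or MAP, no covariate and no repeated-measures method.

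**The concern.** There are three loose ends, all on secondary outcomes.

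- **Schedule.** The outcome list names times at which the procedures plan no reading. Either those outcomes will be missing, or staff will record at times of their own choosing.
- **Baseline.** Both the block and the defined baseline reading come before induction, in an order the plan does not state. If the reading follows the block, it may already carry part of the block's effect. It would then be a poor covariate. It would also be a doubtful reference for the fentanyl rule, because the trigger level could differ between arms and feed into intraoperative opioid requirement.
- **Precision.** A pre-block value is already on the monitor, but the plan names no use for it in the comparison. With 15 or 18 patients per arm, a covariate that explains some of the variation between patients could narrow the interval at very little cost.

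**Working it through.** **Inputs.** Patients per arm: n = 15 (Randomization section) or n = 18 (Sample size section, after the dropout allowance). The two disagree, which is a separate matter, so both are used. The plan gives no mean, SD, correlation or power for HR or MAP. There is thus no stated figure to reproduce, and r, the correlation between the pre-block and the later reading, is an assumption shown over a range.

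**1. Schedules side by side** (both counted from incision, 4-hour operation)

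- Outcome list: 0, 15, 30, 45, 60, 90, 120, 180, 240 min.
- Procedures: just before incision, then 30, 60, 90, 120, 150, 180, 210, 240 min.
- Only in the outcome list: 15 and 45 min. Only in the procedures: 150 and 210 min.

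Moving the origin does not help. A 30-minute grid that contains 0, 30 and 60 cannot also contain 15 and 45. The Measured Parameters section asks only for haemodynamics throughout surgery and does not settle it.

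**2. Position of the baseline.** The holding-room reading precedes the block in the order of the text. The defined baseline has only to precede induction. A reading before the block and one after it both satisfy that wording.

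**3. Fentanyl trigger.** The threshold is 1.2 × baseline. If a post-block baseline differed between arms by an amount d, the threshold would differ by 1.2d. For an assumed d of 5 mmHg, that is 1.2 × 5 = 6 mmHg. A pre-block baseline is free of any block effect.

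**4. Precision at one time point.** Variance of the adjusted group difference relative to the unadjusted one:

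ratio = (1 − r²) × (1 + 1/(2n − 4))

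The second factor is 1 + 1/32 = 1.031 at n = 18 and 1 + 1/26 = 1.038 at n = 15.

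| r | n = 18 | change | n = 15 | change |
|---|---|---|---|---|
| 0 | 1.031 | +3% | 1.038 | +4% |
| 0.1 | 1.021 | +2% | 1.028 | +3% |
| 0.2 | 0.990 | −1% | 0.997 | 0% |
| 0.3 | 0.938 | −6% | 0.945 | −6% |
| 0.5 | 0.773 | −23% | 0.779 | −22% |
| 0.7 | 0.526 | −47% | 0.530 | −47% |

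Setting the ratio to 1 gives r² = 1/(2n − 3), so the break-even r is √(1/33) = 0.174 at n = 18 and √(1/27) = 0.192 at n = 15. As 95% interval width (square root of the ratio, times the t quantile on 2n − 3 df over that on 2n − 2 df), the result is about 2% wider at r = 0, 3% narrower at r = 0.3 and 12% narrower at r = 0.5.

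**5. Effect of treating low MAP.** In a simulation of 20,000 trials with MAP floored at 70 (assumed baseline mean 95, intraoperative mean 80, both SD 12, no true difference), underlying r of 0.1, 0.3, 0.5 and 0.7 gave ratios of 1.023, 0.955, 0.799 and 0.572 at n = 18, and 1.034, 0.953, 0.801 and 0.567 at n = 15. The gain shrinks slightly and no bias appears. The fentanyl and atropine rules were not modelled, so this says nothing about HR.

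**6. Mean over k readings.** With correlation ICC among the later readings, u = (1 + (k − 1) × ICC)/k and the ratio is (u − r²)/u, before the small loss for one degree of freedom.

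- k = 4, ICC = 0.5, r = 0.3: u = 0.625, ratio = 0.535/0.625 = 0.856.
- k = 8, ICC = 0.5, r = 0.5: u = 0.5625, ratio = 0.3125/0.5625 = 0.556.

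Under these assumptions, averaging over times does not weaken the case made at one time point.

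**The case against.** The strongest reply is that this is mostly an optional refinement. The planned tests are valid, the trial is powered on morphine, and HR and MAP are one item among five secondary outcomes. Any gain needs r above roughly 0.2 between an awake reading and readings under isoflurane, fentanyl, ephedrine and atropine, and the documents offer no evidence on r. That stands, and it is why the gain is called possible. The cost side does not depend on r in the same way: at worst, 3 to 4% of variance is lost.

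It can also be said that a repeated-measures model needs more than a sentence. It needs a covariance structure, a small-sample degrees-of-freedom method, and a rule for late times that only long operations reach. This is fair, and the fix covers it.

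A reader might infer that the plan commits to a separate test at every time, at least 7 × 2 = 14 in a 2-hour operation. It does not say so. The Statistical analysis section is a general list, and unadjusted comparison at each time is only an inference from its silence.

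A reader might also infer that the defined baseline is taken after the block. The text leaves this open. The holding-room reading is itself before induction and could be the one meant.

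**Conclusion.** The point holds as a low-cost improvement confined to secondary outcomes. The documents establish three things: the 15 and 45 min readings are named as outcomes but not scheduled, the baseline is not placed relative to the block, and no baseline covariate or repeated-measures analysis is named for HR and MAP.

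The precision gain is conditional. It rests on an assumed r and on the single-time formula: a small loss at r = 0, break-even at r of 0.17 to 0.19, and close to a quarter of the variance saved at r = 0.5.

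No between-arm bias in HR, MAP or fentanyl use has been shown. The differing trigger is a risk only if the baseline is taken after the block and the two blocks act differently on HR or MAP by then. The documents establish neither. Using a pre-block value removes the question.

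**What to change.** 1. **Baseline.** Record one HR and one MAP value in the holding room before midazolam and the block, and define it as the single baseline. Use it both as the covariate and as the reference for the 20% fentanyl rule. Any later pre-induction reading can be kept as a measurement but not called baseline.
2. **Schedule.** Use the same intraoperative times in the Study Protocol and Secondary outcome(s) sections, and define time 0, for example as the reading just before incision. Either add 15 and 45 min to the procedures or drop them from the outcome list. The VAS times need the same check: 30 min and 8 h appear only in the outcome list.
3. **Analysis.** Pre-specify one repeated-measures model for HR and one for MAP, with group, time, group by time and the baseline value. Limit it to fixed times that nearly all operations reach, for example up to 120 min. Make the mean group difference over those times the main comparison and treat the group by time term as supportive. State the covariance structure and the degrees-of-freedom method.

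**Cost.** A short paragraph of text, one noted value per variable per patient from monitoring already in place, and one model per variable. No extra patients or visits are needed. Adding 15 and 45 min means two more readings per operation; dropping them means none.

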### Measured Parameters:

- Hemodynamics including MAP and HR throughout the surgery
- VAS (at rest and cough), MAP, and HR will be noted immediately on arrival to ICU (0 h) and at 2, 4, 6, 12,18, and 24 h postoperatively figure (1).

[figure not shown]

Figure1:Visual analog score (8)

- **Post-operative Total amount of morphine consumption in the first 24-hour.**
- Incidence of complications, such as nerve injury, hematoma formation, and severe hypotension will be noted.

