## **VI. Study outcomes**

### **1. Primary outcome**

- **Total amount of morphine consumption in the first 24-hour postoperative in the two groups.**

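### The scheduled heart rate and MAP readings do not reliably capture the response to incision and rib spreading, so a null haemodynamic comparison would be hard to interpret

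*Combined protocol and SAP*

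**What the plan says.** Three places in the combined protocol and SAP describe the intraoperative readings.

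- **Study Procedures, Study Protocol.** The baseline is defined first: "One reading of MAP and HR will be taken before induction of GA to be defined as a baseline reading". HR and MAP "then will be recorded immediately before surgical incision and at 30 min intervals intraoperatively".
- **Measured Parameters.** "Hemodynamics including MAP and HR throughout the surgery", with no times.
- **Secondary outcomes.** "Heart rate and MAP at 0 , 15min, 30min, 45min, 60min, 90min, 120min, then every 1h intraoperative". Time 0 is not defined.

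Two other provisions bear on the point. Under Study Protocol, extra fentanyl "IV will be given if the mean arterial blood pressure (MAP) or heart rate (HR) rises above 20% of baseline levels", once other causes of the rise have been excluded. The secondary outcomes also include "Opioid requirements intraoperatively".

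The primary outcome is postoperative: "Total amount of morphine consumption in the first 24-hour postoperative in the two groups".

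**The concern.** The trial asks whether splitting the local anaesthetic between two planes gives a more solid block than one plane alone. During surgery, a difference in block quality would be expected to show most clearly when the stimulus is strongest, at skin incision and rib spreading. The plan's own fentanyl rule treats a rise in HR or MAP, with other causes excluded, as a reason to give more analgesia.

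No scheduled reading is tied to the minutes after either event. The one reading anchored to surgery is taken just before the knife. Choosing one of the two lists would not cure this, because neither contains an early post-incision value.

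What is at stake is the meaning of a null result. If the recorded values mostly reflect settled anaesthesia, or a response already treated with fentanyl, the arms may look alike whether or not one block suppressed the stimulus better.

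**Working it through.** The plan states no figure on this point, so there is none to reproduce. The check has three steps.

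**1. Delay from incision to the first later reading**

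| Start of clock | Study Protocol (every 30 min) | Secondary outcomes (0, 15, 30, 45, 60, 90, 120 min, then hourly) |
|---|---|---|
| Pre-incision reading | 30 min | 15 min |
| 10 min before incision | 20 min | 5 min |
| 20 min before | 10 min | 10 min |
| 30 min before | 30 min | 15 min |
| 40 min before | 20 min | 5 min |
| 50 min before | 10 min | 10 min |
| 60 min before | 30 min | 30 min |

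The lags of 10 to 60 min are assumptions standing for a clock started at, say, induction. Each delay is the first scheduled time after the lag, minus the lag. For a 40 min lag on the outcome list, for example, 45 − 40 = 5 min. With an earlier time 0 the delay is therefore not fixed. It can be as short as 5 min in this grid, but it varies between patients, so a given nominal time mixes surgical stages.

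**2. How much of a brief response is left**

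Assume that the response starts at incision and fades with half-life h. The fraction left at time t is 2^(−t/h).

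| h (assumed) | left at 15 min | left at 30 min |
|---|---|---|
| 3 min | 0.03 | 0.001 |
| 5 min | 0.125 | 0.016 |
| 10 min | 0.35 | 0.125 |
| 30 min | 0.71 | 0.50 |

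To illustrate the effect on power, assume a true difference of 10 mmHg between arms in peak MAP and an SD of 12 mmHg. Take 16 per arm (the calculated minimum in the Sample size section) and a two-sided t-test at 0.05.

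- At the peak: d = 10/12 = 0.83, power about 0.63. With 15 per arm (Randomization section) it is 0.60; with 18 (Sample size section, allowing for dropouts) it is 0.68.
- At 15 min, h = 10: difference 3.5 mmHg, d = 0.29, power about 0.13. With h = 3 the difference is 0.3 mmHg and power about 0.05.
- At 30 min, h = 10: difference 1.25 mmHg, d = 0.10, power about 0.06.
- At 15 min, h = 30: difference 7.1 mmHg, d = 0.59, power about 0.36.

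If the clock is unrelated to incision, with the offset uniform over the interval g between readings, the average fraction left at the first reading is (1 − 2^(−g/h)) / (g ln 2 / h). For h from 3 to 10 min this is 28 to 62% with g = 15 and 14 to 42% with g = 30. More of the response is then recorded, but at different nominal times in different patients.

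**3. What the fentanyl rule does to the record**

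The trigger operates at any time in surgery, so HR and MAP have to be watched between scheduled readings. A patient whose rise passes 20% may be treated before the next scheduled value. That response then appears as a dose in the intraoperative opioid outcome, but the plan does not require its HR and MAP values or its timing relative to incision to be recorded. A rise that stays below 20% triggers nothing and can be missed altogether.

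**The case against.** The strongest reply is that the trial already captures the response that matters. A rise above 20% triggers fentanyl, and intraoperative opioid requirement is a listed outcome. A reader might infer from the schedules that the response to incision is never recorded, or that the readings bear no relation to surgery. The documents support neither inference. Marked responses are captured indirectly as fentanyl use, one reading is anchored to incision, and a clock started earlier could put a reading soon after it. Rib spreading is not timed in the plan, so a reading at 15 or 30 min could coincide with it. Nor does the continuous monitoring mentioned under Study Protocol settle how often values are recorded during surgery, because that sentence concerns the holding room.

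It is also fair to say that the plan never calls HR and MAP a measure of block quality. They could serve safety, since hypotension and bradycardia are listed complications, and regular readings suit that purpose. The power figures rest wholly on an assumed half-life, difference and SD, and they model incision only.

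These points limit the claim without removing it. Fentanyl use gives a dose without the HR and MAP values or the link to incision, and it says nothing of smaller responses. A reading that falls near the stimulus by chance is not a planned comparison. And HR and MAP are listed as outcomes in their own right, so a comparison of them will presumably be reported and interpreted.

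**Conclusion.** The point holds in limited form. Intraoperative HR and MAP are secondary outcomes, and the scheduled readings do not reliably capture the response to incision and rib spreading. On a clock starting at the pre-incision reading, the first later value is 30 min away under Study Protocol and 15 min away under the outcome list. On an earlier clock the timing varies by patient. A finding of no haemodynamic difference would therefore be hard to interpret.

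The size of the loss cannot be fixed from the documents. It is severe if the response fades within minutes (at most about 35% left at 15 min for half-lives up to 10 min) and moderate if it lasts (71% left at 15 min with a 30 min half-life). The 24-hour morphine comparison is unaffected. This is a worthwhile refinement of a secondary outcome; it does not threaten the trial's main conclusion.

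**What to change.** - Reconcile the readings under Study Protocol and Secondary outcomes into one schedule, with time 0 at skin incision. Keep the pre-induction and pre-incision readings.
- Add a few readings shortly after incision and after rib spreading, for example at 1, 5 and 10 min, taken from the monitoring that the fentanyl rule already requires.
- Record the time of rib spreading and of every intraoperative fentanyl bolus.
- Prespecify the change from the pre-incision value over this early window as a supportive HR/MAP comparison, read together with intraoperative fentanyl use. It should not be the main haemodynamic contrast, because triggered fentanyl alters the values and noting the dose does not undo that.

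The cost is a few extra recorded values per patient and short edits in two sections. No treatment rule changes.
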